Aim 3. Preliminary effectiveness of the MeSSSSage intervention components on six-month MCH outcomes. Using the quantitative survey data, we will statistically evaluate differences by study arm in improvements in women's knowledge, behaviors, and maternal and child health outcomes, compared to the control group (including effect sizes, controlling for relevant socio-demographics as necessary). Figure 1 displays the outcomes that are theoretically related to our intervention targets. Our main *knowledge* outcome will be a composite score representing the proportion of correct answers from a knowledge scale on breastfeeding, newborn and infant care, maternal and infant danger signs, newborn care, and family planning, topics that will be covered within our interactive educational group component. Our main *behavior* outcome will be self-reported exclusive breastfeeding at 6 months. Our main *health related* outcomes will be: (1) completion of early childhood immunization schedule; and (2) postnatal family planning uptake. We will measure women's social support and related mental health status (depression and anxiety) using scales that have been previously validated in similar populations such as the Hopkins Symptom Checklist⁴¹ and the Multidimensional Scale of Perceived Social Support⁴². Finally, women's empowerment will be measured using decision-making and mobility scales.^{43,44}

Sample Size. This pilot development study is not formally powered to detect significant differences in outcomes, but will give insight into directionality of changes. The per group sample size was selected based on feasibility

of recruitment, intervention delivery, and the interpersonal interaction important for a group-focused intervention. The sample is sufficiently large to assess the feasibility and acceptability outcomes through descriptive statistics.

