Text-based, asynchronous, on-demand social support: App-based small group text-based communication. Moderated by health professional. (text)		X	X	
Standard of care: 3 visits in the first 7 days postnatal (facility and home)	X	X	X	X

The following intervention characteristics will be assessed:

Feasibility. To evaluate feasibility of the intervention, we will monitor enrollment rates and moderator effort required (e.g. number of staff hours). An enrollment rate of 70% or higher will be considered feasible, as the established standard in intervention literature. Through moderator report we will confirm effort required for preparation, session delivery, and follow-up. We will also capture any technological challenges. This information will inform staffing needs and retention protocols for a subsequent full trial.

Acceptability. To measure acceptability, we will use a client satisfaction questionnaire which will capture self-reported engagement in intervention components and topics, satisfaction with intervention components, likelihood of participating again, likelihood of recommending program, and value on knowledge and social support gained from participation.

Preliminary effectiveness. To measure effectiveness, we will health-related knowledge (maternal and neonatal danger signs, best practices for infant care, and family planning), health-related behaviors (breastfeeding and complementary food introduction practices (breastfeeding initiation, length of exclusive breastfeeding, length of breastfeeding, timing of complementary food introduction), appropriate management of early childhood

illnesses), and health outcomes (Early childhood immunization, postnatal depression and anxiety, postnatal contraceptive adoption.)

Quantitative analyses: With a between-groups design, each participant will participate in only one arm of the trial, thus we will assess quantitative intervention outcomes by factor (voice and text) through fitting a series of the following linear regression model:

$$y_i = \beta_0 + \beta_1 Z_{1i} + \beta_2 Z_{2i} + \beta_3 Z_{1i}Z_{2i} + \varepsilon_i$$

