Where y_i is the outcome for the i^{th} participant, β_0 is the coefficient for the intercept (standard of care), β_1 represents the mean difference in factor 1 (voice), β_2 represents the mean difference in factor 2, (text) β_3 represents the interaction between factor 1 and factor 2 (voice + text), Z_{1i} is the indicator variable for factor 1, Z_{2i} is the indicator variable for factor 2, and ε_i is the residual for the i^{th} participant. Due to the modest sample size, significance testing will be deemphasized and we have not included power analyses for this study.

Hypotheses for preliminary/exploratory analyses on effectiveness. Exploratory hypotheses will be evaluated as part of the study feasibility assessment process. Means and proportions will be plotted by group over time to enable descriptive evaluation of overall patterns of change across time in the outcomes for the intervention and control groups. For example, we expect that following intervention exposure, relative to control group participants, intervention participants will have improved health-related knowledge, health-related behavior, and health outcomes. We also anticipate that intervention participants receiving both voice and text components will have the highest report of the prior outcomes and reported social support, and we will explore differences in these outcomes and in levels of reported social support between the groups as described above.

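### The SAP promises effects by factor, but β1 and β2 in its 0/1 interaction model are voice-only and text-only versus control, so no coefficient gives the factor effect unless the interaction is zero

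*SAP*

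**What the plan says.** The SAP (Statistical Design and Power, Quantitative analyses) sets the target: "we will assess quantitative intervention outcomes by factor (voice and text". The model is y = β0 + β1Z1 + β2Z2 + β3Z1Z2 + ε. Its terms are described as follows, taken here in a different order from the SAP's.

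- Coding: the SAP says of Z1 that it "is the indicator variable for factor 1". Z2 has the same role for text.
- Product term: the SAP's description of its coefficient, β3, is that it "represents the interaction between factor 1 and factor 2 (voice + text".
- Voice: the label attached to β1 is that it "represents the mean difference in factor 1 (voice". The label on β2 has the same form, with text in place of voice.
- Intercept: β0 is tied to the women who receive standard of care only, which makes control the reference arm.

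The protocol repeats this text under its own Statistical Design and Power heading. Two other statements bear on the target. The protocol's Analysis section for Aim 3 says "we will statistically evaluate differences by study arm", with control as the comparator and effect sizes reported. The SAP's paragraph on hypotheses expects that "intervention participants receiving both voice and text components will have the highest report of the prior outcomes". The same paragraph plans plots of the outcomes for each group.

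**The concern.** In a 2x2 factorial, the effect of a factor is usually the difference between women with and without it, averaged over the levels of the other factor. The SAP's stated target and its labels for β1 and β2 can be read that way. The coding cannot deliver it: with 0/1 indicators and a product term, β1 and β2 are effects in the absence of the other component.

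An analyst who follows the text would therefore either report the voice-only difference under the name of the voice factor effect, or report differences from control and leave the by-factor assessment undone. Significance testing is deemphasized, so the effect estimates and their names are the main output of Aim 3. The protocol intends the results to inform the design of a larger trial, so a component effect should go forward under a name that says what was estimated.

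**Working it through.** **Inputs.** The coding, intercept and product term are from the SAP, Quantitative analyses. The size is 160 women, 40 per arm (Protocol, Aim 2), and 4 x 40 = 160 agrees. The plan states no power, effect size or SD, so there is no such figure to reproduce. Results below are in units of the residual SD.

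**Step 1: arm means implied by the model.**

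| Arm | Z1 | Z2 | Mean |
|---|---|---|---|
| Control | 0 | 0 | β0 |
| Arm 1 (voice) | 1 | 0 | β0 + β1 |
| Arm 2 (text) | 0 | 1 | β0 + β2 |
| Arm 3 (both) | 1 | 1 | β0 + β1 + β2 + β3 |

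**Step 2: contrasts.**

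- Arm 1 - Control = β1, and Arm 2 - Control = β2.
- Voice factor effect = ½[(Arm 1 - Control) + (Arm 3 - Arm 2)] = ½[β1 + (β1 + β3)] = β1 + β3/2.
- Text factor effect = ½[(Arm 2 - Control) + (Arm 3 - Arm 1)] = β2 + β3/2.
- Arm 3 - Control = β1 + β2 + β3.
- Arm 3 - Arm 1 = β2 + β3, and Arm 3 - Arm 2 = β1 + β3.

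So β1 minus the voice factor effect is -β3/2, and the same holds for β2 and text.

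**Step 3: numerical check.** The printed model was fitted by least squares to invented arm means of 10 (Control), 13 (voice), 12 (text) and 20 (both), 40 women per arm. It returns β0 = 10, β1 = 3, β2 = 2 and β3 = 20 - 13 - 12 + 10 = 5. The voice factor effect is (13 + 20)/2 - (10 + 12)/2 = 5.5 = 3 + 5/2. The text factor effect is (12 + 20)/2 - (10 + 13)/2 = 4.5 = 2 + 5/2. With additive means 0, 1, 1, 2 the fit gives β3 = 0, and β1 and β2 both equal the factor effects, 1.

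**Step 4: size, with β3 assumed.**

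| Assumed β3 (SD) | -0.4 | -0.2 | 0 | +0.2 | +0.4 |
|---|---|---|---|---|---|
| β1 - factor effect = -β3/2 | +0.20 | +0.10 | 0 | -0.10 | -0.20 |

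For example, assume voice alone +0.30, text alone +0.30 and both +0.40 SD. Then β3 = 0.40 - 0.30 - 0.30 = -0.20, β1 = 0.30, and the voice factor effect is 0.30 - 0.10 = 0.20.

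**Step 5: precision**, with 40 per arm, independent women and full follow-up.

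- β1, β2 or Arm 3 - Control: √(2/40) = 0.224 SD.
- A factor effect, 80 versus 80: √(2/80) = 0.158 SD.
- β3: √(4/40) = 0.316 SD.

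**The case against.** The labels can be defended. The intercept is defined as standard of care and Z1 and Z2 as indicators alongside them, so a mean difference for voice may simply mean the difference from standard of care. On that reading β1 and β2 are correct, and they serve the protocol's by-arm aim. Neither document speaks of a main or averaged effect. This stands, and it is why the point is one of ambiguity. It does not supply the by-factor estimate, which on this reading no coefficient gives.

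A reader might infer more than the documents support:

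- **That the model is wrong.** It is not. Four parameters fit four arm means, and every contrast above can be recovered from it.
- **That β3 is presented as the effect of the combined arm.** It is called an interaction, and the words in parentheses most naturally name the two factors that interact. A clearer description is a precaution.
- **That the combined arm is never compared with control.** The protocol's Aim 3 analysis already plans arm-versus-control comparisons; only the expression in model terms is missing.
- **That the expectation for voice plus text cannot be examined.** The planned arm means allow it.
- **That β1 never draws on Arm 3.** This is true only of the unadjusted point estimate. Arm 3 contributes to the pooled residual variance and, if the socio-demographic adjustment allowed in the protocol is used, to the covariate slopes.
- **That the larger standard error of β1 is a fault.** β1 and the factor effect are different estimands.

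It is also fair to say that the gaps in Step 4 rest on assumed β3 values and are smaller than one standard error of β1 (0.224 SD).

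**Conclusion.** The point holds as a minor labelling and estimand issue. As coded, the unadjusted β1 and β2 are voice-only and text-only versus control. They equal the factor effects only when β3 = 0, and otherwise differ from them by β3/2. Read as differences from standard of care, the labels are right, but the by-factor estimate is then given by no coefficient. Either way the stated target and the listed coefficients need to be reconciled.

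The β3/2 gap is algebra and does not depend on sample size or independence. Its numerical size does depend on β3, for which the documents give no value: 0.10 to 0.20 SD in absolute terms for assumed interactions of 0.2 to 0.4 SD in either direction. With a standard error of 0.316 SD for β3, the pilot could hardly distinguish such interactions from zero, so the gap cannot be assumed away from the data. Aim 3 is exploratory and unpowered, and no sample size or decision rule depends on this.

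**What to change.** Keep the model and the definition of β0. In the SAP's Quantitative analyses and the matching protocol paragraph:

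1. Label β1 as voice-only versus control and β2 as text-only versus control. This ties the model to the by-arm comparison in the protocol's Aim 3 analysis.
2. For the by-factor assessment, report β1 + β3/2 and β2 + β3/2 with 95% confidence intervals. State that each averages over the other factor, uses all four arms, and is to be read alongside β3, which is imprecisely estimated.
3. Give β1 + β2 + β3 as voice plus text versus control, and describe β3 as departure from additivity.

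Optionally, add β2 + β3 (Arm 3 minus Arm 1) and β1 + β3 (Arm 3 minus Arm 2) for the expectation that voice plus text does best.

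The cost is a few sentences in each document. Every quantity is a linear combination from the fit already planned, so no further data, participants or refitting are needed.

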Table 1: Modalities to be explored to identify optimal intervention functions, processes and platforms (Phase 1).

Modality	Description of modalities	Goal
Group structure	(1) Frequency: How often groups are held (2) Length: How long groups last (3) Timing: What time of day/day of week	To determine the best group structure
Participants	(1) Number (2) Breadth of gestational age (3) Age of respondents	To determine the best group structure
Group Interaction type	(1) Women have to “raise their hand” virtually, by typing a specified number into their phones if they have a question or comment, and then the moderator gives “permission” to women to speak one by one (2) Open line where women can speak at any point. (3) Moderator call out individual women to ask if they have questions or comments	To measure: 
• Level of comfort with participation• Amount of engagement and interactions between participants• Conversation dominated by certain participants• Communication patterns
Content	(1) Additional information desired (2) Level of detail of information (3) Language and approach used by moderators	To adjust and expand the content/topics covered
Text-based group addition	Offer an additional freer-form, ongoing, text-based group (e.g., WhatsApp)	To determine: 
• Number of interactions• Barriers for women with low literacy• Group sense of support

Procedures: Primiparous women will be recruited in their last month of pregnancy by the ASHA and a research assistant during the ASHA’s regular home visit. At enrollment, the study protocol and informed consent will be described to the women, written informed consent will be obtained from interested women, and phone numbers collected (and tested). Women who do not personally own a phone will be provided with one. Airtime for all participants will be covered during this 2-month preliminary phase. Consent will also be obtained from family members per local cultural practices. Consent will cover phase 1 intervention and the evaluation components.

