Table 2: *MeSSSSage* components to be tested in feasibility and acceptability assessment (Phase 2).

	Arm 1	Arm 2	Arm 3	Control
Real-time live voice call group meeting: Interactive educational program with scripted didactic component plus discussion/question. Lead and moderated by health professional.	X		X	
Text-based, asynchronous, on-demand social support: App-based small group text-based communication. Moderated by health professional.		X	X	
Standard of care: 3 visits in the first 7 days postnatal (facility and home)	X	X	X	X

Procedures: Unless found not feasible or acceptable within Phase 1 activities, women will be recruited using the approach described above (Aim 1). At the time of enrollment, the study protocol will be described to the women per informed consent procedures. Written confirmation will be obtained from interested women and their phone numbers will be collected (and tested). Women without a phone will be provided with a phone and all participants' airtime will be covered for the length of the 6-month research project. Women who consent will be randomly enrolled into 1 of the 4 study arms using a random number generator. We will test each study condition using 2 groups of women, with intervention initiation staggered 1 month apart. Women in the control group will receive the standard of care. All women will be given 50 Indian Rupees for participation in each session (in addition to airtime and phone if needed), and ASHAs will receive 150 Indian Rupees for moderating each session. Assessment of feasibility and acceptability (Aim 2) and preliminary effectiveness (Aim 3) will be accomplished using mixed-methods including quantitative surveys, in-depth interviews, and technology assessment.

Survey data collection: Baseline and endline surveys will be administered by a research assistant in the respondent's home. Endline survey will be collected roughly 6 months postnatal, after potential participation in ~24 *MeSSSSage* sessions (details to be determined during Phase 1). We will capture women's health record cards and ASHA registers to validate self-reported health outcome data. Data will be collected on a tablet using the secure REDCap mobile research administration app, stored in a password protected database at UCSF, and no identifiable information will be included with analytic datasets (identifiable data will be stored separately).

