Sociodemographic characteristics	Age, age at marriage, educational attainment, caste, language spoken, household assets, women's status/decision-making, social support and relationship quality.
Health-related knowledge (effectiveness)	Knowledge on maternal and neonatal danger signs, best practices for infant care, family planning.
Health-related behaviors (effectiveness)	Breastfeeding and complementary food introduction practices (breastfeeding initiation, length of exclusive breastfeeding, length of breastfeeding, timing of complementary food introduction), appropriate management of early childhood illnesses.
Health outcomes (effectiveness)	Early childhood immunization, postnatal depression and anxiety, postnatal family planning adoption.
Intervention perspectives (feasibility, acceptability)	Self-reported engagement in intervention components and topics, satisfaction with intervention components, likelihood of participating again, likelihood of recommending program, value on knowledge and social support gained from participation.

Analysis. *Aim 2. Feasibility and acceptability of the optimized MeSSSSage intervention components.* We will use a mixed methods approach, triangulating data from quantitative baseline and endline data, qualitative IDIs, and technology assessment. Feasibility and acceptability will be measured by participation rates at each session, participation trajectories over time, and user engagement (via technology assessment backend data). Women's reports of use and satisfaction (survey and IDI will shed light on barriers and facilitators to participation. Moderator acceptability will be assessed by satisfaction, fidelity to topic/content based on protocol and perspectives on impact. We will test for differences in feasibility and acceptability between the three intervention arms to understand if both components (group meetings and text) or only one is the best approach, using ANOVA for continuous outcomes and chi-square or Fisher's exact tests, as appropriate, for categorical outcomes.

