Recruitment. Study participants will be recruited by a team consisting of an Accredited Social Health Activists (ASHA) and a research assistant, overseen by the SWACH project and principal investigators. ASHAs are familiar with the women in this study population, as they already provide information and support about health to them in the community. Primiparous women will be recruited in their last month of pregnancy during the ASHA's regular home visit. At the time of enrollment, the study protocol will be described to the women following informed consent procedures and written informed consent will be obtained from interested women. Consent will also be obtained from family members given the cultural practices in the study population. Names and contact information will be collected and stored in a password protected and encrypted computer in a locked facility.

For Aims 2 and 3 (Piloting the intervention), We will recruit for the three intervention and the one control arms using a staggered approach, recruiting one group for each arm in month one of the intervention period and one group for each arm in month two of the intervention period, to result in a total of eight groups (two per condition), for a total of 160 participants. Such a staggered approach is preferred to ensure that women are enrolled into groups with other women whose infants are similarly aged, and is feasible given the population size of our study districts.

Retention plan (i.e. Attrition reduction plan). We will carefully monitor attrition in this study.

Retention is facilitated by engagement of the ASHA, who has familiarity and experience working with the community, and previous knowledge of the participants. Contact information, including names, addresses, and phone numbers, will be collected at baseline to facilitate tracking. One of the aims of this study is to measure participation and engagement in the intervention, thus, we will be measuring retention as one of our outcomes.

PROTECTION OF HUMAN SUBJECTS

Risks to Human Subjects

Human Subjects Involvement and Characteristics of Potential Subjects

The proposed two phased project will enroll a total of (160+48) women to develop the optimal design and then understand the acceptability, feasibility, and preliminary effectiveness of the MeSSSSage intervention on maternal and infant health outcomes in India.

Inclusion criteria are:

Phase 1: 18+ years old, primiparous (pregnant with their first birth)

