Feasibility. To evaluate feasibility of the intervention, we will monitor enrollment rates and moderator effort required (e.g. number of staff hours). An enrollment rate of 70% or higher will be considered feasible, as the established standard in intervention literature. Through moderator report we will confirm effort required for preparation, session delivery, and follow-up. We will also capture any technological challenges. This information will inform staffing needs and retention protocols for a subsequent full trial.

Acceptability. To measure acceptability, we will use a client satisfaction questionnaire which will capture self-reported engagement in intervention components and topics, satisfaction with intervention components, likelihood of participating again, likelihood of recommending program, and value on knowledge and social support gained from participation.

Preliminary effectiveness. To measure effectiveness, we will health-related knowledge (maternal and neonatal danger signs, best practices for infant care, and family planning), health-related behaviors (breastfeeding and complementary food introduction practices (breastfeeding initiation, length of exclusive breastfeeding, length of breastfeeding, timing of complementary food introduction), appropriate management of early childhood

illnesses), and health outcomes (Early childhood immunization, postnatal depression and anxiety, postnatal contraceptive adoption.)

Quantitative analyses: With a between-groups design, each participant will participate in only one arm of the trial, thus we will assess quantitative intervention outcomes by factor (voice and text) through fitting a series of the following linear regression model:

$$y_i = \beta_0 + \beta_1 Z_{1i} + \beta_2 Z_{2i} + \beta_3 Z_{1i}Z_{2i} + \varepsilon_i$$

Where y_i is the outcome for the i^{th} participant, β_0 is the coefficient for the intercept (standard of care), β_1 represents the mean difference in factor 1 (voice), β_2 represents the mean difference in factor 2, (text) β_3 represents the interaction between factor 1 and factor 2 (voice + text), Z_{1i} is the indicator variable for factor 1, Z_{2i} is the indicator variable for factor 2, and ε_i is the residual for the i^{th} participant. Due to the modest sample size, significance testing will be deemphasized and we have not included power analyses for this study.

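### Women in the intervention arms are treated in about two discussion groups of 20 per arm, but the analysis treats them as independent, so standard errors are too small if outcomes are positively correlated within groups

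*SAP*

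**What the plan says.** Protocol, Phase 2 Procedures, has consenting women allocated one by one to four arms with a random number generator. Treatment is then given in groups: "We will test each study condition using 2 groups of women, with intervention initiation staggered 1 month apart". The Recruitment section agrees, "recruiting one group for each arm in month one of the intervention period and one group for each arm in month two", giving eight groups and 160 participants. Both components are group-based and moderated by a health professional. Controls receive standard of care.

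For Aim 3, the Quantitative analyses paragraph (the same in protocol and SAP) bases the model on a between-groups design: "each participant will participate in only one arm of the trial, thus we will assess quantitative intervention outcomes by factor". The model contains voice, text, their interaction and an error that "is the residual for the i^{th} participant".

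For Aim 2, the protocol's Analysis section says "We will test for differences in feasibility and acceptability between the three intervention arms", "using ANOVA for continuous outcomes and chi-square" or Fisher's exact test for categorical outcomes.

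No group effect, ICC, design effect or robust variance appears in either document. The only adjustment offered is for socio-demographics.

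**The concern.** Individual randomisation makes women independent at allocation, but not after six months of shared sessions, a shared moderator and shared group discussion. The protocol gives grounds to expect group effects. Its Sample Size section cites "the interpersonal interaction important for a group-focused intervention" as a basis for the group size. Table 1 lists "Conversation dominated by certain participants" among the things to measure in Phase 1, which is weaker, secondary support. The Aim 2 outcomes (session participation, engagement, satisfaction) are those a lively or quiet group would shift most directly.

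With two groups per arm, a difference between arms may be no more than a difference between two active groups and two quiet ones. The Aim 2 tests are meant to show whether one component or both works best, and the results are to inform the design of a larger trial. Standard errors that are too small would overstate how well this pilot separates the arms. Without an ICC, the follow-on trial would also lack a planning figure it needs.

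**Working it through.** **Inputs from the documents.** 160 women, 40 per arm (Specific Aims, Aim 2); eight groups, two per condition (Recruitment). The sizes agree: 4 × 40 = 160, and 160 / 8 = 20 women per group. There is no power or precision figure to reproduce.

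**Assumptions.** The documents state no ICC, test level or interval level. I take ICC from 0.01 to 0.10, a two-sided 5% level and 95% intervals for illustration. Controls are taken as unclustered, because they have no group sessions.

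**Formulas.** With m = 20, the design effect is D = 1 + 19 × ICC. The true standard error divided by the independence standard error is:

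- intervention arm versus intervention arm: √D
- intervention arm versus control (β1, β2): √((D + 1)/2)
- interaction (β3): √((3D + 1)/4)

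At ICC 0.05, D = 1 + 0.95 = 1.95. The ratios are √1.95 = 1.40, √1.475 = 1.21 and √1.7125 = 1.31. Coverage of a nominal 95% interval between two intervention arms is approximately 2Φ(1.96/√D) − 1.

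**Results.** False-positive rates come from 40,000 simulated null trials per setting (three arms × two groups × 20, plus 40 controls), with the whole ICC specific to the group. Chi-square assumes 70% prevalence.

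| | ICC 0.01 | 0.02 | 0.05 | 0.10 |
|---|---|---|---|---|
| D | 1.19 | 1.38 | 1.95 | 2.90 |
| Effective n per arm of 40 (40/D) | 33.6 | 29.0 | 20.5 | 13.8 |
| Three-arm ANOVA | 8% | 12% | 22% | 37% |
| Three-arm chi-square | 8% | 12% | 22% | 37% |
| β1, voice versus control | 6% | 7% | 11% | 17% |
| β3, interaction | 7% | 8–9% | 14% | 21–22% |
| Coverage between two intervention arms | 93% | 90% | 84% | 75% |

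At ICC 0 the ANOVA and regression tests reject at about 5%, so the excess comes from clustering alone.

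**Start month.** Each arm has one group per month, so a common month effect cancels from contrasts between intervention arms. If half of the ICC is due to month, the ANOVA rates fall to about 6 / 8 / 13 / 22%. If all of it is, they stay at or below 5%. The table is therefore the upper case for each ICC.

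**Can six groups support a correction?** An F test on group means (2 and 3 df) holds about 5% at every ICC when there is no month effect. It is conservative (3.3–4.5%) when half the ICC is due to month. With month in the model (2 and 2 df) it holds about 5% in both cases. The price is precision: the critical F is 9.55 on 2 and 3 df, against 3.07 for the planned 2 and 117 df. The ICC itself is poorly estimated. With a true ICC of 0.05 the estimate is zero or negative in 31% of trials, and its central 95% range is about −0.04 to 0.22.

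**The case against.** The strongest reply is that little rests on these tests. The plan says the pilot is not powered, that significance testing will be played down, and that feasibility and acceptability can be judged descriptively. That stands, and it limits the severity. It does not remove the fault: Aim 2 still plans tests between arms, Aim 3 plans statistical comparisons with effect sizes, and any interval attached to them uses the same standard errors.

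Other points stand in part:

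- **Direction.** Only positive correlation makes the standard errors too small. For a quantity shared out in a fixed session, such as speaking time, domination by a few women could make the correlation negative.
- **Group size.** Twenty is the planned figure and still provisional. Smaller analysed groups soften the effect: with 14 per group and ICC 0.05, the ANOVA rate is about 16–17%.
- **Weak remedies.** Six groups cannot support a reliable variance component. With one arm shifted by 0.5 SD and ICC 0, the group-mean test has about 27–28% power, against 62% for the planned ANOVA. This argues for leading with descriptive group-level results, not for keeping the independence analysis.
- **Moderators.** The documents do not say how facilitators are assigned to groups. If one facilitator runs both groups of an arm, no group term can separate facilitator from arm.

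**Conclusion.** The concern holds. As written, the regression and the Aim 2 tests ignore group delivery, and their standard errors are too small whenever within-group correlation is positive. The comparison among the three intervention arms suffers most, and comparisons with control less. At an assumed group-specific ICC of 0.05 with groups of 20, standard errors should be 1.40 times larger between intervention arms and 1.21 times larger against control. The nominal 5% ANOVA rejects about 22% of the time. The size depends on the ICC, on how much of it is due to start month, and on the 5% and 95% levels, none of which the documents give. Point estimates, control-only estimates and the 70% enrolment criterion are not affected. The aims are exploratory and no confirmatory claim depends on these tests, so this is a should-fix point.

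**What to change.** - **Aim 2:** present arm differences descriptively, with the six group values shown. If a test is wanted, base it on group means or proportions, with 2 and 3 df, or 2 and 2 df if start month is included.
- **Regression:** add a random intercept for discussion group in the intervention arms only (a partially nested model), with small-sample degrees of freedom. Report the ICC with its interval and say that it is imprecise.
- **Sensitivity:** also give intervals at fixed ICCs, for example 0.01, 0.05 and 0.10. With six groups the estimated group variance will often be zero, and the fitted model then returns the naive interval.
- **Facilitators:** state how they are assigned to groups, and note the limit on interpretation if facilitator and arm coincide.
- **Number of groups:** reconcile the Phase 2 overview, which gives three groups per modality and eight in total, with the two per condition in Procedures and Recruitment. Three groups in each of three intervention arms would already make nine. The degrees of freedom depend on the answer; with three groups of 13 per arm and ICC 0.05, the ANOVA rate is about 16%.

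The cost is SAP wording, a little more analysis and wider intervals. No further data or participants are needed.
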